5.7 Management of Biological Samples

5.7.1 Storage, re-use and destruction of biological samples

Samples will be stored for a maximum of 15 years from the date of the Last Subject's Last Visit, after which they will be destroyed. The results of this biomarker research will be reported either in the Clinical Study Report itself or as an addendum, or separately in a scientific report or publication. The results of this biomarker research may be pooled with biomarker data from other studies with the study drug to generate hypotheses to be tested in future research.

5.7.2 Labelling and shipment of biological samples

The Principal Investigator ensures that samples are labelled and shipped in accordance with the Laboratory Manual and the Biological Substance, Category B Regulations (materials containing or suspected to contain infectious substances that do not meet Category A criteria), see [Appendix C](#) 'IATA 6.2 Guidance Document'.

Any samples identified as Infectious Category A materials are not shipped and no further samples will be taken from the subject unless agreed with AstraZeneca and appropriate labelling, shipment and containment provisions are approved.

All tumour samples should be shipped at ambient temperature as per the Laboratory Manual to the AstraZeneca designated central Contract Research Organisation.

5.7.3 Chain of custody of biological samples

A full chain of custody is maintained for all samples throughout their lifecycle.

The Principal Investigator at each centre keeps full traceability of collected biological samples from the subjects while in storage at the centre until shipment or disposal (where appropriate) and keeps documentation of receipt of arrival.

The sample receiver keeps full traceability of the samples while in storage and during use until used or disposed of or until further shipment and keeps documentation of receipt of arrival.

AstraZeneca keeps oversight of the entire life cycle through internal procedures, monitoring of study sites and auditing of external laboratory providers.

Samples retained for further use are registered in the AstraZeneca Biobank during the entire life cycle.

5.7.4 Withdrawal of informed consent for donated biological samples

If a subject withdraws consent to the use of donated biological samples, the samples will be disposed of/destroyed, and the action documented. If samples are already analysed, AstraZeneca is not obliged to destroy the results of this research.

The Principal Investigator:

- Ensures subjects' withdrawal of informed consent to the use of donated samples is notified immediately to AstraZeneca
- Ensures that biological samples from that subject, if stored at the study site, are immediately identified, disposed of /destroyed, and the action documented
- Ensures the laboratory(ies) holding the samples is/are informed about the withdrawn consent immediately and that samples are disposed of/destroyed, the action documented and the signed document returned to the study site
- Ensures that the subject and AstraZeneca are informed about the sample disposal.

AstraZeneca ensures the central laboratory(ies) holding the samples is/are informed about the withdrawn consent immediately and that samples are disposed of/destroyed and the action documented and returned to the study site.

AstraZeneca ensures that biological samples are destroyed at the end of a specified period as described in the informed consent.

5.8 Post progression outcomes

The date of second progression will be recorded by the Investigator and defined according to local standard clinical practice and may involve any of; objective radiological or symptomatic progression or death. Second progression status will be reviewed every 6 weeks following the progression event used for the primary variable PFS (the first progression) and status recorded. To support PFS2, the time to start of subsequent treatment will be recorded.

6. SAFETY REPORTING AND MEDICAL MANAGEMENT

The Principal Investigator is responsible for ensuring that all staff involved in the study are familiar with the content of this section.

6.1 Definition of adverse events

An adverse event is the development of an undesirable medical condition or the deterioration of a pre-existing medical condition following or during exposure to a pharmaceutical product, whether or not considered causally related to the product. An undesirable medical condition can be symptoms (e.g., nausea, chest pain), signs (e.g., tachycardia, enlarged liver) or the abnormal results of an investigation (e.g., laboratory findings, electrocardiogram). In clinical studies, an AE can include an undesirable medical condition occurring at any time, including run-in or washout periods, even if no study treatment has been administered.

The term AE is used to include both serious and non-serious AEs.

For cases where it could be suspected that a tissue-derived medicine has been contaminated by a pathogen, information about any of the above conditions (including infection) should be

collected. Any deterioration of the disease targeted in the study and associated symptoms should not be regarded as an adverse event as far as the deterioration can be anticipated.

6.2 Definitions of serious adverse event

A serious adverse event is an AE occurring during any study phase (i.e., run-in, treatment, washout, follow-up), that fulfils one or more of the following criteria:

- Results in death
- Is immediately life-threatening
- Requires in-patient hospitalisation or prolongation of existing hospitalisation
- Results in persistent or significant disability/incapacity or substantial disruption of the ability to conduct normal life functions
- Is a congenital abnormality or birth defect
- Is an important medical event that may jeopardise the subject or may require medical intervention to prevent one of the outcomes listed above.

For further guidance on the definition of a SAE, see [Appendix B](#) to the Clinical Study Protocol.

6.3 Recording of adverse events

6.3.1 Time period for collection of adverse events

Adverse Events will be collected from time of signature of informed consent throughout the treatment period and including the safety follow-up period. The follow-up period is defined as 28 days after study treatment is discontinued. SAEs occurring in the follow-up period should be reported to AstraZeneca in the usual manner (see Section [6.4](#)).

Following discontinuation of AZD9291, SAEs considered related to study procedures should continue to be collected as outlined in [Table 8](#).

After the final database lock, there may be some patients remaining on study treatment. For these patients who are continuing to receive AZD9291 AstraZeneca will collect information (during the treatment period and for 28 days after last dose) on SAEs, deaths (including those due to disease progression), discontinuation due to AEs/SAEs and drug accountability only.

Table 8 Summary of recording and follow-up of adverse events and deaths

	Consent to Treatment Period	Until 28-day Follow-up Visit (safety follow-up period)	Post 28-day Follow-up visit but prior to progression (if applicable)	Post 28-day Follow-up visit and post progression (survival follow-up period)
Collect all new AEs in CRF	Yes	Yes	No	No
Collect all ongoing AEs in CRF	Yes	Yes	Yes	Yes
Collect all study procedure-related SAEs in CRF	Yes	Yes	Yes	Yes
Death due to AE, or unknown cause¹	Yes	Yes	No	No

¹ for example, death not due to disease progression, refer to Section [6.3.10](#)

6.3.2 Follow-up of unresolved adverse events

Any AEs that are unresolved are followed up by the investigator for as long as medically indicated. AstraZeneca retains the right to request additional information for any patient with ongoing AE(s) at the end of the study, if judged necessary.

If an investigator learns of any SAEs, including death, at any time and he/she considers there is a reasonable possibility that the event is related to AZD9291, the investigator should notify AstraZeneca.

6.3.3 Variables

The following variables will be collect for each AE;

- AE (verbatim)
- The date when the AE started and stopped
- Maximum CTCAE grade/changes in CTCAE grade
- Whether the AE is serious or not
- Investigator causality rating against the Investigational Product (yes or no)
- Action taken with regard to investigational product
- Outcome.

In addition, the following variables will be collected for SAEs:

- Date AE met criteria for serious AE

- Date Investigator became aware of serious AE
- AE is serious due to
- Date of hospitalisation
- Date of discharge
- Causality assessment in relation to Study procedure(s)
- Causality assessment in relation to other medication
- Description of AE.

It is important to distinguish between serious and severe AEs. Severity is a measure of intensity whereas seriousness is defined by the criteria in Section 6.2. An AE of severe intensity need not necessarily be considered serious. For example, rash that covers >30% of the body may be considered severe, but not a SAE unless it meets the criteria shown in Section 6.2. On the other hand, a stroke that results in only a limited degree of disability may be considered a mild stroke but would be a SAE when it satisfies the criteria shown in Section 6.2.

The grading scales found in the current National Cancer Institute CTCAE version 4 will be utilised for all events with an assigned CTCAE grading. For those events without assigned CTCAE grades, the recommendation in the CTCAE criteria that converts mild, moderate and severe events into CTCAE grades should be used. A copy of the current CTCAE version can be downloaded from the Cancer Therapy Evaluation Program website (<http://ctep.cancer.gov>).

6.3.4 Causality collection

The Investigator will assess causal relationship between Investigational Product and each Adverse Event, and answer 'yes' or 'no' to the question 'Do you consider that there is a reasonable possibility that the event may have been caused by the investigational product?'

For SAEs causal relationship will also be assessed for other medication and study procedures. Note that for SAEs that could be associated with any study procedure the causal relationship is implied as 'yes'.

A guide to the interpretation of the causality question is found in [Appendix B](#) to the Clinical Study Protocol.

6.3.5 Adverse events based on signs and symptoms

All AEs spontaneously reported by the subject or care provider or reported in response to the open question from the study personnel: 'Have you had any health problems since the previous visit/you were last asked?', or revealed by observation will be collected and recorded in the CRF. When collecting AEs, the recording of diagnoses is preferred (when possible) to recording a list of signs and symptoms. However, if a diagnosis is known and there are other

signs or symptoms that are not generally part of the diagnosis, the diagnosis and each sign or symptom will be recorded separately.

6.3.6 Adverse events based on examinations and tests

The results from protocol mandated laboratory tests and vital signs will be summarised in the clinical study report. Deterioration as compared to baseline in protocol-mandated parameters should therefore only be reported as AEs if they fulfil any of the SAE criteria or are the reason for discontinuation of treatment with the investigational product unless clearly due to progression of disease under study (see Section 6.3.8).

If deterioration in a laboratory value, vital sign, ECG, or other safety assessment is associated with clinical signs and symptoms, the sign or symptom will be reported as an AE and the associated laboratory result or other finding will be considered as additional information. Wherever possible the reporting Investigator uses the clinical, rather than the laboratory term (e.g., anaemia versus low haemoglobin value). In the absence of clinical signs or symptoms, clinically relevant deteriorations in non-mandated parameters should be reported as AE(s).

Deterioration of a laboratory value, which is unequivocally due to disease progression, should not be reported as an AE/SAE.

Any new or aggravated clinically relevant abnormal medical finding at a physical examination as compared with the baseline assessment will be reported as an AE.

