4.3 Follow-up period

4.3.1 Discontinuation visit

A Discontinuation Visit will be performed at the time AZD9291 is permanently stopped. Refer to [Table 1](#) for full details.

4.3.2 28 Day follow-up

As a minimum, telephone contact should be made with the patient 28 days (+/- 7 days) following the discontinuation of AZD9291 to collect new AEs and follow up on any ongoing AEs and concomitant medications (including any subsequent cancer therapy). Refer to Section 6.3 for full details on AE recordings during follow-up.

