5.2.4 ECG

All patients will have 12-lead digital ECGs performed at the study visits indicated in [Table 1](#). Twelve-lead ECGs will be obtained after the patient has been resting semi-supine for at least 10 minutes prior to times indicated and should be recorded at 25 mm/sec. All ECGs should be recorded with the patient in the same physical position. For each time point three ECG recordings should be taken within an approximate 5 minute period. Digital ECG recordings will be collected, analyzed and stored by a central ECG vendor.

In addition to the ECG requirements outlined in [Table 1](#), the Screening Visit and PK sampling days will require three ECGs to be performed at the following time points shown in [Table 4](#).

Table 4 Digital ECG recording requirements

Time relative to dose	Screening (baseline)	Cycle 1 Day 1	Cycle 2 Day 1	Cycle 3 Day 1
Pre-dose (± 5 min)	X ¹	X	X	X
1 hour (± 5 min)	X	X		X
2 hours (± 10 min)	X	X		X
4 hours (± 10 min)	X	X		X
6 hours (± 10 min)	X	X		X
8 hours (± 10 min)	X	X		X
10 hours (± 10 min)	X			X
12 hours (± 1 hour)	X			X
24 hours (± 1 hour)	X			X (D2, pre-dose)

¹ Since there is no dosing at Screening, ECG recordings should start at a time that would be consistent with planned dosing times at Cycle 1 Day 1, Cycle 2 Day 1 and Cycle 3 Day 1 (for baseline purposes).

After ECGs have been recorded as digital ECG files, a print-out will be made and the investigator or designated physician will review each of the ECGs and may refer to a local cardiologist if appropriate. A paper copy should be filed in the patient's medical records. If an abnormal ECG finding at screening or baseline is considered to be clinically significant by the investigator, it should be reported as a concurrent medical history condition. If there is a clinically significant abnormal ECG findings during the treatment period, this should be recorded on the AE CRF, according to standard adverse events collection and reporting processes.

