6.7 Management of IP related toxicities

If a patient experiences a CTCAE grade 3 or higher and/or unacceptable toxicity (any grade) not attributable to the disease or disease-related processes under investigation, where the Investigator considers the AE of concern to be specifically associated with AZD9291, dosing will be interrupted and supportive therapy administered as required in accordance with local practice/guidelines.

If the toxicity resolves or reverts to \leq CTCAE grade 2 within 3 weeks of onset, treatment with AZD9291 may be restarted at the same dose (80 mg) or a lower dose (40 mg) using the rules below for dose modifications (Table 9) and with discussion and agreement with the AstraZeneca Study Team Physician as needed. There will be no individual modifications to dosing schedule in response to toxicity, only potential dose reduction or dose interruption.

If the toxicity does not resolve to \leq CTCAE grade 2 after 3 weeks, then the patient should be withdrawn from the study and observed until resolution of the toxicity.

Table 9 Dose interventions

Intervention	AZD9291 Dose
Starting Dose	80 mg

Table 9 **Dose interventions**

Intervention	AZD9291 Dose
Reduced Dose –1	40 mg

On resolution of toxicity within 3 weeks:

- If an AE subsequently requires dose interruption, AZD9291 may restart at the same dose or the reduced dose, on resolution/improvement of the AE at the discretion of the Investigator.

If new or worsening pulmonary symptoms (eg, dyspnoea) or radiological abnormality suggestive of interstitial lung disease is observed, an interruption in study treatment dosing is recommended, and the AstraZeneca study team should be informed. A questionnaire regarding the results of the full diagnostic workup (including high-resolution computed tomography (HRCT), blood and sputum culture, haematological parameters) will be sent to Investigators. It is strongly recommended to perform a full diagnostic workup, to exclude alternative causes such as lymphangitic carcinomatosis, infection, allergy, cardiogenic edema, or pulmonary hemorrhage. In the presence of confirmatory HRCT scans where other causes of respiratory symptoms have been excluded, a diagnosis of interstitial lung disease should be considered and study treatment permanently discontinued.

In the absence of a diagnosis of interstitial lung disease study treatment may be restarted following consultation with the AstraZeneca Study Team Physician.

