Patients with QTcF prolongation fulfilling the following criteria (i.e. confirmed QTcF prolongation to > 500 msec absolute or a > 60 msec increase from baseline) should have study treatment interrupted and regular ECGs performed until resolution to baseline. If the toxicity does not resolve to ≤ grade 1 within 3 weeks the patient will be permanently withdrawn from study treatment.

Patients experiencing corneal ulceration or Interstitial Lung Disease (ILD) will not be permitted to restart study treatment.

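### Section 6.3.6 omits dose interruption and dose reduction from the grounds for reporting a test abnormality as an AE, and does not fit with Sections 5.2.4, 6.1 and 6.7

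*Supplement*

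**What the plan says.** The text in force is the protocol of 26 February 2014 as changed by Amendments 1 and 2. Neither amendment touches Section 6.3.6.

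- **Section 6.3.6** notes that mandated laboratory and vital-sign results are summarised in the study report anyway. It concludes, for deteriorations in protocol-mandated parameters, that these "should therefore only be reported as AEs if they fulfil any of the SAE criteria or are the reason for discontinuation of treatment". If the abnormality comes with clinical signs or symptoms, "the sign or symptom will be reported as an AE and the associated laboratory result or other finding will be considered as additional information".
- **Section 6.7** covers CTCAE grade 3 or higher and/or unacceptable toxicity: "where the Investigator considers the AE of concern to be specifically associated with AZD9291, dosing will be interrupted". Treatment may then restart at 80 mg or 40 mg. Patients who meet the QTcF criteria "should have study treatment interrupted and regular ECGs performed until resolution to baseline".
- **Section 5.2.4**, in a sentence that Amendment 1 leaves standing: "If there is a clinically significant abnormal ECG findings during the treatment period, this should be recorded on the AE CRF".
- **Section 6.1** includes abnormal laboratory and ECG results among the conditions that can be AEs.
- **Section 6.3.3**, as amended, collects investigator causality, action taken with the investigational product, and outcome for each AE.

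**The concern.** The dosing section and the reporting section do not fit together. Section 6.7 presupposes an AE that leads to an interruption. Section 6.3.6 does not allow that AE to be reported when the trigger is a silent, non-serious test abnormality and the drug is later restarted.

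Safety and tolerability is a secondary objective and is reported with the primary analysis. There is one arm and no data monitoring committee. Causality, action taken and outcome hang on the AE record, so without a record none of the three is captured for that event. The AE summaries by CTCAE grade would run low selectively, for the kinds of toxicity that can be found by testing without symptoms. For ECG findings, whether an event enters the AE data could depend on which section a site follows.

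**Working it through.** No arithmetic applies: the plan states no figure for this, and none can be derived. The check is to set the passages side by side.

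1. **Does discontinuation cover a temporary stop?** The second ground in Section 6.3.6 is that abnormalities are reportable if they "or are the reason for discontinuation of treatment with the investigational product". Section 4.3.1 fixes the sense of the word: "A Discontinuation Visit will be performed at the time AZD9291 is permanently stopped". Sections 6.7 and 7.2 treat interruption and reduction as separate actions. An interruption followed by a restart therefore does not meet this ground.

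2. **Which events are affected?** Symptomatic abnormalities are reported through the sign or symptom. Serious ones are reported as SAEs. Under Section 6.7, a toxicity that has not recovered within 3 weeks leads to withdrawal, so it meets the discontinuation ground. What remains is the asymptomatic, non-serious abnormality that recovers in time, after which drug is resumed at the same or the lower dose.

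3. **Does Section 6.3.6 really mean to leave these out?** It goes on to say that clinically relevant asymptomatic deteriorations in non-mandated parameters are AEs. That contrast only makes sense if asymptomatic deteriorations in mandated parameters are not AEs, apart from the two listed grounds.

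4. **Is there an overriding rule elsewhere, parameter by parameter?**
   - *Laboratory:* Section 5.2.1 sends the reader back to Section 6.3 for AE recording, so nothing overrides.
   - *LVEF:* the assessment is mandated at screening and every 12 weeks, and Section 5.2.5 has no AE rule of its own. The stated rationale in 6.3.6 names only laboratory tests and vital signs, so the restriction probably covers LVEF, but less certainly.
   - *ECG:* Section 5.2.4 gives the opposite instruction for clinically significant findings. It adds that standard AE processes apply, which a site could read as leading back to Section 6.3. The two sections conflict.
   - *Vital signs:* Section 5.2.6.1 has changes recorded as AEs if applicable, which leaves the matter open.

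5. **What is recorded without an AE?** Section 7.2 puts every interruption and reduction in the eCRF. Section 8.9.2 summarises laboratory data, vital signs, LVEF, exposure and dose delays. ECGs go to a central vendor, and Section 8.9.2 as amended counts patients with QT/QTc above 500 ms or increases above 60 ms. Those are the cut-offs that trigger interruption for QTcF in Section 6.7.

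6. **What is missing?** The event's place in the AE summary by grade, the investigator's causality rating, and the action-taken entry tying the dose change to its cause.

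**The case against.** The strongest reply is that the safety signal survives. Section 6.3.6 gives a reason for the restriction, namely that the results are summarised separately. Laboratory values, QTc outliers and dose changes all reach the database. Section 8.5 provides an expert review of laboratory, vital-sign and ECG data for other significant AEs, and its examples include marked laboratory abnormalities and events leading to dose reduction. The SAE definition takes in important medical events, and Appendix B lists blood dyscrasias such as neutropenia or anaemia requiring transfusion. Transaminase rises to 3 times ULN must be notified under Appendix E. Sites that follow the wording of Section 6.7 may record the event as an AE anyway.

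Most of this stands, and it confines the loss to AE counts and linkage. It does not close the gap. The Section 8.5 review is discretionary, does not name LVEF, and creates no investigator AE record. Under Appendix E, a transaminase rise that does not meet the potential Hy's law criteria is notified and followed, with no AE entry required. That some sites would record the event regardless shows that the rule is not uniform.

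A reader might infer that Section 6.3.6 bars ECG toxicity from the AE data. The documents do not support that: Section 5.2.4 requires clinically significant findings on the AE form, and QTcF prolongation that calls for interruption would ordinarily be one. The fault there is a contradiction.

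**Conclusion.** The point holds for asymptomatic, non-serious laboratory toxicities that lead only to an interruption or a reduction, and probably for LVEF ones. For ECG findings it holds as a conflict between Sections 6.3.6 and 5.2.4. It rests on the literal text of 6.3.6 and on discontinuation meaning a permanent stop.

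The size cannot be estimated, because the documents give no rate for such events and do not show how sites would resolve the conflict. A reader might infer that real toxicities could appear as zero in 175 patients and then be read, through Section 8.2, as a true rate below 2.2%. That would need an assumed event rate, every site leaving out every such event, and an analyst disregarding the laboratory and QTc tables. Nothing in the documents supports that chain.

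Nor is the absence of a table of AEs by dose action a fault. Section 8.9.2 leaves the detail of safety summaries to the SAP, which is not shown. ORR is unaffected. This is a reporting weakness in a secondary objective, worth correcting because the correction is small.

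**What to change.** In Section 6.3.6, add interruption and dose reduction of the investigational product to discontinuation as grounds for reporting a deterioration in a protocol-mandated parameter as an AE. Reconcile that section with 5.2.4, 6.1 and 6.7, so that one AE-reporting rule applies to laboratory, LVEF and ECG findings, and cross-refer to it from 5.2.4. State explicitly whether LVEF counts as a protocol-mandated parameter for this purpose. Align the CRF completion guidance.

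This changes what is reported, not how patients are dosed, and no view is taken on the dosing rules. The cost is a short amendment and a guidance update, with a few more AE entries and a slightly higher reported AE rate. The existing per-AE fields in Section 6.3.3 then capture causality and action taken without new data collection.
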